5.2 Exclusion Criteria

The participant must be excluded from the study if the participant meets any of the following criteria:

Medical Conditions

1. For Cohort D and F (DLBCL and NHL): Has lymphoplasmacytic lymphomas, Waldenstrom's macroglobulinemia, chronic lymphocytic leukemia (not associated with small lymphocytic lymphoma), Burkitt (-like) lymphoma, mature T-cell and NK cell neoplasms, immunodeficiency associated lymphoproliferative neoplasms, or histiocytic and dendritic cell neoplasms.
2. For Cohort E (MM):
 - a) Has oligo-secretory myeloma, plasma cell leukemia, smoldering multiple myeloma, monoclonal gammopathy of undetermined significance.
 - b) History of primary amyloidosis, hyperviscosity or POEMS syndrome (plasma cell dyscrasia with polyneuropathy, organomegaly, endocrinopathy, monoclonal protein, and skin changes).
3. For Cohort F (EBV+ DLBCL): For patients with EBV+ DLBCL should NOT be associated with a solid organ transplant.
4. Has known prior or current CNS involvement.
5. A WOCBP who has a positive urine pregnancy test within 72 hours before study intervention allocation (see Appendix 5). If the urine test is positive or cannot be confirmed as negative, a serum pregnancy test will be required.

Note: If 72 hours have elapsed between the screening pregnancy test and the first dose of study intervention, another pregnancy test (urine or serum) must be performed and must be negative in order for participant to start receiving study medication.

6. Has clinically significant cardiovascular disease within 12 months from first dose of study intervention, including New York Heart Association Class III or IV congestive heart failure, unstable angina, myocardial infarction, cerebral vascular accident, or cardiac arrhythmia associated with hemodynamic instability.

Note: Medically controlled arrhythmia would be permitted.

7. Has a history or current evidence of any condition, therapy, or laboratory abnormality that might confound the results of the study, interfere with the participant's participation for the full duration of the study, or is not in the best interest of the participant to participate, in the opinion of the treating investigator.
8. Has a history of a second malignancy, unless potentially curative treatment has been completed with no evidence of malignancy for 3 years.

Note: The time requirement does not apply to participants who underwent successful definitive resection of basal cell carcinoma of the skin, squamous-cell carcinoma of the skin, superficial bladder cancer, in situ cervical cancer, or other in situ cancers.

Prior/Concomitant Therapy

9. Has received prior therapy with an mAb blocking TIGIT, an anti-TIGIT agent or an agent modulating the TIGIT axis, or an anti-PD-1, anti-PD-L1, or anti-PD-L2 agent (except where specified) or with an agent directed to another stimulatory or coinhibitory T-cell receptor (eg, CTLA-4, OX-40, CD137).

Note: Participants in Cohort B, relapsed or refractory cHL or PMBCL, must have been previously treated with an anti-PD-1/L1 agent.

Note: Participants with toxicities to prior anti-PD-1/L1 therapy will be excluded unless their toxicities have resolved to \leq Grade 1 and/or permanent discontinuation is mandated per [Table 11](#). Exceptions include participants with Grade 1-4 hypothyroidism, Grade 2 hyperthyroidism, and Grade 2 hyperglycemia (in combination with evidence of β -cell failure).

10. Any PMBCL participants in Cohort A and B that require the use of urgent cytoreductive therapy.

11. Has received prior systemic anticancer therapy, including investigational agents, within 2 weeks (small molecules like kinase inhibitors) or 4 weeks (chemotherapies and monoclonal antibodies) before cohort allocation.

Note: Participants must have recovered from all AEs due to previous therapies to \leq Grade 1 or baseline. Participants with \leq Grade 2 neuropathy may be eligible. Participants with endocrine-related AEs \leq Grade 2 requiring treatment or hormone replacement may be eligible. For consideration of AEs related to previous treatment with anti-PD-1/L1 therapies, see note below criterion #9 above.

12. If the participant had major surgery, the participant must have recovered adequately from the procedure and/or any complications from the surgery before starting study intervention.

13. Has received prior radiotherapy within 2 weeks of start of study intervention. Participants must not require ongoing corticosteroid use, and not have $>$ Grade 1 radiation pneumonitis or other radiation-related toxicities. A 1-week washout is permitted for palliative radiation (\leq 2 weeks of radiotherapy) to non-CNS disease.

14. Has received a live or live-attenuated vaccine within 30 days before the first dose of study intervention. Administration of killed vaccines is allowed. Refer to Section 6.5 for information on COVID-19 vaccine.

Prior/Concurrent Clinical Study Experience

15. Is currently participating in or has participated in a study of an investigational agent or has used an investigational device within 4 weeks before the first dose of study intervention.

Note: Participants who have entered the follow-up phase of an investigational study may participate as long as it has been 4 weeks after the last dose of the previous investigational agent

Diagnostic Assessments

16. Known severe hypersensitivity to MK-7684A, vibostolimab or pembrolizumab and/or any of its excipients.
17. Has a known history of HIV infection. No HIV testing is required unless mandated by local health authority. Refer to Appendix 7 for country-specific testing requirements.
18. Has an active autoimmune disease that has required systemic treatment in past 2 years (ie, with use of disease modifying agents, corticosteroids or immunosuppressive drugs). Replacement therapy (eg, thyroxine, insulin, or physiologic corticosteroid replacement therapy for adrenal or pituitary insufficiency) is not considered a form of systemic treatment and is allowed.
19. Has an active infection requiring systemic therapy.
20. Has a history or current evidence of any condition, therapy, or laboratory abnormality that might confound the results of the study, interfere with the participant's participation for the full duration of the study, or is not in the best interest of the participant to participate, in the opinion of the treating investigator.
21. Has a known psychiatric or substance abuse disorder that would interfere with the participant's ability to cooperate with the requirements of the study.
22. Has present or progressive accumulation of pleural, ascitic, or pericardial fluid requiring drainage or diuretic drugs within 2 weeks before enrollment.
23. Has dual active HBV infection (HBsAg (+) and /or detectable HBV DNA) and HCV infection (anti-HCV Ab (+) and detectable HCV RNA) at study entry.

Other Exclusions

24. Participant, in the judgment of the investigator, is unlikely to comply with the study procedures, restrictions, and requirements of the study.
25. Has had an allogenic hematopoietic stem cell/solid organ transplantation within the last 5 years. Participants who have had a transplant greater than 5 years ago are eligible as long as there are no symptoms of Graft versus Host Disease

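### Read literally, the note to exclusion 9 does not exclude a Cohort B participant whose earlier anti-PD-1/L1 toxicity required a permanent stop under Table 11 and has since resolved

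*Combined protocol and SAP*

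**What the plan says.** Section 5.2, exclusion 9, bars prior treatment with checkpoint agents except where specified. Cohort B is the specified exception: prior anti-PD-1/L1 treatment is required there. A note then deals with toxicity from that treatment. It begins "Participants with toxicities to prior anti-PD-1/L1 therapy will be excluded unless their toxicities have resolved to", where the level required is Grade 1 or lower. A second condition follows in the same clause, in the words "Grade 1 and/or permanent discontinuation is mandated per", with Table 11 as the reference. The note then lists its exceptions: "Exceptions include participants with Grade 1-4 hypothyroidism, Grade 2 hyperthyroidism, and Grade 2 hyperglycemia" (the last with evidence of β-cell failure).

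Exclusion 11 has a general recovery rule, "Participants must have recovered from all AEs due to previous therapies to" Grade 1 or lower or baseline. It closes with a hand-over: "For consideration of AEs related to previous treatment with anti-PD-1/L1 therapies, see note below criterion #9 above".

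Table 11 (Section 6.6.3) lists the events that require permanent discontinuation. They include recurrent Grade 2 or any Grade 3 or 4 pneumonitis, and Grade 3 or 4 nephritis. Section 5 does not allow waivers of entry criteria.

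**The concern.** A toxicity severe enough to require a permanent stop is normally a reason to keep a patient away from the same drug class. The note lists it instead among the conditions that lift the exclusion. MK-7684A contains pembrolizumab, so entry means renewed PD-1 blockade with vibostolimab added. Safety and tolerability is the primary objective of Part 1 (Section 3), and with waivers ruled out sites must apply the criterion as printed. What is at stake is protection of participants at entry. No estimator, analysis population or sample size depends on the sentence.

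**Working it through.** No arithmetic applies; the check is of the sentence's logic and of the criteria around it.

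**1. Truth table.** Let R mean the toxicity has resolved to Grade 1 or lower, and S mean Table 11 mandates a permanent stop for it. The evident intent is to exclude if (not R) or S, so that only R without S may enter. The literal text can be taken three ways:

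- L1: *and/or* means *or*, and exclusion 11 leaves anti-PD-1/L1 events to the note. Not excluded if R or S.
- L2: *and/or* means *or*, and exclusion 11's recovery rule still applies. Not excluded if (R or S) and R, which reduces to R.
- L3: *and/or* means *and*. Not excluded if R and S, whichever way exclusion 11 is taken.

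| Case | Intended | L1 | L2 | L3 |
|---|---|---|---|---|
| R, S | excluded | not excluded | not excluded | not excluded |
| R, no S | not excluded | not excluded | not excluded | excluded |
| no R, S | excluded | not excluded | excluded | excluded |
| no R, no S | excluded | excluded | excluded | excluded |

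The first row is wrong in every literal column. The second is wrong only under L3 and the third only under L1. (For simplicity the table ignores exclusion 11's alternative of recovery to baseline.)

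**2. Does another visible criterion close the first row?**

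- Exclusion 11 asks only for recovery, which a resolved event satisfies.
- Exclusion 6, "Has clinically significant cardiovascular disease within 12 months from first dose of study intervention", may catch recent myocarditis but not pneumonitis or nephritis.
- Exclusion 16, "Known severe hypersensitivity to MK-7684A, vibostolimab or pembrolizumab and/or any of its excipients", is confined to hypersensitivity.
- Exclusion 18, "Has an active autoimmune disease that has required systemic treatment in past 2 years", concerns active autoimmune disease and does not name a resolved immune-related event.
- Exclusions 7 and 20 (identical text) reach medical history but rest on the investigator's opinion.
- Section 7.1 requires a permanent stop for toxicity from study intervention, not from earlier therapy.

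None is a rule tied to Table 11. Table 8 and Appendix 7, which holds country-specific Cohort B requirements, are redacted and cannot be checked.

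**3. Can the case arise?** Section 5.1 (Cohort B, items 2c and 2h) requires at least 2 anti-PD-1/L1 doses and progression during therapy or within 12 weeks of the last dose. It allows other treatments in between. A patient who stopped for toxicity and then progressed inside that window can qualify, and the interval leaves time for the toxicity to resolve.

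**4. Which meaning was intended?** Table 11 says to continue treatment for Grade 2 hyperthyroidism and Grade 2 to 4 hypothyroidism, and it does not list Grade 2 hyperglycemia for a permanent stop. It would be odd to exempt these milder events by name if permanent-stop events were already exempt.

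**The case against.** The strongest reply is that a sensible reader supplies the missing words: excluded unless resolved, and also excluded where a permanent stop is mandated. On that elliptical reading the resolved permanent-stop case is kept out, and the endocrine exceptions support it. This stands as evidence of intent, and it means one cannot say that every possible reading admits the case; only the literal ones do. It does not rescue the sentence, because the words it needs are not there and a safety exclusion should not depend on sites supplying them.

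A reader might also infer that unresolved permanent-stop toxicity is let in. The documents do not support that as a firm finding. It requires taking *and/or* as *or* and also reading exclusion 11's last sentence as switching off its own recovery rule.

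Safeguards can be cited. Exclusions 7 and 20 cover history, and a qualified physician reviews eligibility (Section 8.1.2), so some such enrolments would be stopped, but by discretion. Section 10.3.5 requires the Sponsor Clinical Director's advance approval for risky rechallenge. That text sits within causality assessment and follows a question about re-exposure in this study, so its use at entry is doubtful.

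It is also fair that the affected group is narrow. Cohort B's lead-in calls for progression on treatment, and few or no participants may have stopped for toxicity and still qualify. Finally, the Amendment 5 wind-down may mean enrolment is over, although the documents do not say so. If it is, new wording protects nobody and only reporting remains.

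**Conclusion.** The note is wrong as written: a drafting error in an operative safety criterion. The firm finding is one case, a Table 11 permanent-stop toxicity that has resolved to Grade 1 or lower. It is not excluded under either literal meaning of *and/or*, and no other visible criterion excludes it by rule.

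The scope is Cohort B, about 30 participants in Part 1, and more only if the optional Part 2 opens. The number affected cannot be found from the documents and may be zero. The documents do not show that any such participant was enrolled or harmed, and no analysis is affected.

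The conclusion assumes that the redacted Table 8 and Appendix 7 add no relevant bar, and that the intent was to exclude permanent-stop toxicities, which the note's own exceptions support.

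**What to change.** In the note to exclusion 9, end the first sentence after Grade 1, delete the *and/or* limb, and add: *Participants whose prior toxicity is one for which Table 11 mandates permanent discontinuation will be excluded even if it has resolved.* Keep the endocrine exceptions. The cost is one sentence turned into two, with no new data or procedures.

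If enrolment has closed, report in the CSR any Cohort B participants who can be identified, from the collected medical history and prior-therapy records, as having had such an event. State that the list may be incomplete. Section 8.1.4 captures resolved conditions only if diagnosed within the prior 10 years and judged clinically important by the investigator. It does not ask for grade or attribution to anti-PD-1/L1 therapy, both of which are needed to apply Table 11.

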5.3 Lifestyle Considerations

5.3.1 Meals and Dietary Restrictions

Participants should maintain a normal diet unless modifications are required to manage an AE such as diarrhea, nausea, or vomiting.

5.3.2 Caffeine, Alcohol, and Tobacco Restrictions

No restrictions are required.

5.3.3 Activity Restrictions

No restrictions are necessary.

5.4 Screen Failures

[figure not shown]
Screen failures are defined as participants who consent to participate in the clinical study but are not subsequently entered in the study. A minimal set of screen-failure information is required to ensure transparent reporting of screen-failure participants to meet the CONSORT publishing requirements and to respond to queries from regulatory authorities. Minimal information includes demography, screen-failure details, eligibility criteria, and any AEs or SAEs meeting reporting requirements as outlined in the data entry guidelines.

Participants who fail screening may be rescreened for eligibility after consultation between the investigator and the Sponsor and written documentation of the collaborative decision on participant management.

5.5 CCI [REDACTED]

5.5.1 CCI [REDACTED]

CCI [REDACTED]

6 STUDY INTERVENTION

Study intervention is defined as any investigational intervention(s), marketed product(s), placebo, or medical device(s) intended to be administered to a study participant according to the study protocol.

Clinical supplies MK-7684A coformulation will be packaged to support enrollment. Clinical supplies will be affixed with a clinical label in accordance with regulatory requirements.

6.1 Study Intervention(s) Administered

The study interventions to be used in this study are outlined in [Table 9](#)

All study interventions will be administered in the clinic setting.

Table 9 Study Interventions

Arm Name	Arm Type	Intervention Name	Intervention Type	Dose Formulation	Unit Dose Strength(s)	Dosage Level(s)	Route of Administration	Regimen/ Treatment Period/ Vaccination Regimen	Use	IMP or NIMP/ AxMP	Sourcing
Part 1: Cohorts A to F	Experimental	MK-7684A	Biological/Vaccine	Injection, Solution	Vibostolimab 200mg+ pembrolizumab 20 mg/ 20mL vial	200 mg/ 200 mg	IV Infusion	Q3W up to 35 cycles	Test Product	IMP	Central

EEA=European Economic Area, IMP=investigational medicinal product; IV=intravenous; NIMP/AxMP=noninvestigational/auxiliary medicinal product; Q3W=every 3 weeks.

The classification of IMP and NIMP in this table is based on guidance issued by the European Commission and applies to countries in the EEA. Country differences with respect to the definition/classification of IMP/NIMP may exist. In these circumstances, local legislation is followed.

MK-7684A = coformulated as 200 mg vibostolimab and 200 mg pembrolizumab

Only participants that achieved SD, PR, or CR after initial treatment or first course followed by an investigator-determined disease progression as per disease-specific criteria will be eligible for a second course of treatment.

All supplies indicated in **Table 9** will be provided per the “Sourcing” column depending on local country operational requirements. If local sourcing, every attempt should be made to source these supplies from a single lot/batch number.

Refer to Section 8.1.9 for details regarding administration of the study intervention.

6.1.1 Initial Treatment or First Course

The initial treatment or first course of MK-7684A coformulation consists of 35 treatments, administered Q3W. Note: The number of treatments is calculated starting with the first dose.

For participants who have attained a CR (confirmation of CR is required for MM participants) and have been treated for at least 8 cycles (at least 24 weeks) beyond the initial CR date (initial CR confirmation date for MM participants), treatment may be stopped.

6.1.2 Second Course of Study Treatment

All participants who have SD, PR, or CR may be eligible for up to an additional 17 cycles of MK-7684A if there is investigator-determined disease progression as per disease-specific criteria (see Appendix 8) after initial treatment or first course has been completed or stopped for confirmed CR, PR or SD. This retreatment is the second course of this study.

Note: For participants in Cohort E (MM), confirmation of CR is required beyond the initial CR date.

Participants may enter the second course if all of the following criteria are met:

1. No new anticancer treatment was administered after the last dose of study intervention
2. The participant meets all of the inclusion criteria and none of the exclusion criteria
3. The study is ongoing

An objective response or disease progression that occurs during the second course will not be counted as an event for the primary analysis of either endpoint in this study.

6.2 Preparation/Handling/Storage/Accountability

6.2.1 Dose Preparation

Details on preparation and administration of MK-7684A are provided in the Pharmacy Manual.

6.2.2 Handling, Storage, and Accountability

The investigator or designee must confirm appropriate temperature conditions have been maintained during transit for all study intervention received, and any discrepancies are reported and resolved before use of the study intervention.

Only participants enrolled in the study may receive study intervention, and only authorized site staff may supply or administer study intervention. All study interventions must be stored in a secure, environmentally controlled, and monitored (manual or automated) area in accordance with the labeled storage conditions with access limited to the investigator and authorized site staff.

The investigator, institution, or the head of the medical institution (where applicable) is responsible for study intervention accountability, reconciliation, and record maintenance (ie, receipt, reconciliation, and final disposition records).

For all study sites, the local country Sponsor personnel or designee will provide appropriate documentation that must be completed for drug accountability and return, or local discard and destruction if appropriate. Where local discard and destruction is appropriate, the investigator is responsible for ensuring that a local discard/destruction procedure is documented.

The study site is responsible for recording the lot number, manufacturer, and expiry date for any locally purchased product (if applicable) as per local guidelines unless otherwise instructed by the Sponsor.

The investigator shall take responsibility for and shall take all steps to maintain appropriate records and ensure appropriate supply, storage, handling, distribution, and usage of study interventions in accordance with the protocol and any applicable laws and regulations.

6.3 Measures to Minimize Bias: Randomization and Blinding

6.3.1 Intervention Assignment

Participants enrolled in Part 1 of the study will be assigned to receive study intervention within the appropriate cohort as described in Section 5.1.

6.3.2 Stratification

No stratification based on age, sex, or other characteristics will be used in this study.

6.3.3 Blinding

This is an open-label study; therefore, the Sponsor, investigator, and participant will know the intervention administered.

6.4 Study Intervention Compliance

If there are interruptions in the study intervention schedule, the details of and reason for any interruption of study intervention will be documented in the participant's medical record.

Refer to Section 6.6.2 for dose modification and toxicity management for irAEs associated with MK-7684A and for other allowed dose interruptions of MK-7684A.

Participants will receive study intervention in the clinic setting directly from the investigator or designee, under medical supervision. The date and time of each dose administered in the clinic will be recorded in the source documents and recorded in the CRF. The dose of study intervention and study participant ID will be confirmed at the time of dosing by a member of the study-site staff other than the person administering the study intervention.

6.5 Concomitant Therapy

[figure not shown]
Medications or vaccinations specifically prohibited in the exclusion criteria are not allowed during the treatment period. If there is a clinical indication for any medication or vaccination specifically prohibited, discontinuation from study therapy or vaccination may be required. The investigator should discuss any questions regarding this with the Sponsor's Clinical Director. The final decision on any supportive therapy or vaccination rests with the investigator and/or the participant's primary physician. However, the decision to continue the participant on-study intervention requires the mutual agreement of the investigator, the Sponsor, and the participant.

All treatments that the investigator considers necessary for a participant's welfare may be administered at the discretion of the investigator in keeping with the community standards of medical care. All concomitant medications will be recorded on the eCRF including all prescriptions, OTC products, herbal supplements, and IV medications, and fluids. If changes occur during the study period, documentation of drug dosage, frequency, route, and date should also be included on the eCRF.

[figure not shown]
All concomitant medications received within 28 days prior to the first dose of study intervention and up to 30 days after the last dose of study intervention should be recorded. All concomitant medications administered during SAEs or ECIs are to be recorded. SAEs and ECIs are defined in Section 8.4.

